In this experimental investigation we will gather data to describe the mean changes in balance and gait behavior from baseline for two treatment groups. The results will inform the design and power of subsequent, incremental studies investigating the clinical efficacy of this intervention. Standardized clinical assessment mechanisms will measure changes in balance, gait, cognition, emotional function, headache, eye movement, and sleep in individuals with post-concussive and post-traumatic stress complaints in a 14-week rehabilitation program and after a 12-week withdrawal period.

Study Design

The randomized double blind study will enroll up to 44 subjects (males and females) with identified balance deficits that will be equally distributed into 2 subgroups: an “Active” CN-NINM device (PoNS) group, and a “Control” (very low stimulation) device group. Subjects will be randomly assigned to one of the two treatment groups by the Clinical Monitor as they are recruited using a rolling recruitment method. Cohort assignment will be made by serially selecting from a list of 44 randomly generated three-digit subject identification numbers, with 22 assigned to both the Active and Control group.

The study will be a total of 26 weeks, consisting of three stages. The first stage consists of twice-daily in-lab training (ITP) for 2-weeks (with at-home training during the intervening weekend). The intensive CN-NINM training program will focus on balance and gait. This is followed by the second stage, which consists of subjects performing the same training for 12 weeks during Stage 2 – the Home Training Program (HTP). During this second stage, subjects will return to the lab 1

time per week for a training session. After completion of the second stage, subjects continue in the third stage, the withdrawal stage, where they no longer use the PoNS device.

Multiple assessment metrics will capture data at important points during the study: at the beginning and end of the 2-week in-lab CN-NINM intervention period (ITP), every 3 weeks of the test/retraining intervals during the home training phase (HTP) and every 3 weeks of the withdrawal phase. This will yield a total of 10 data points for each subject on the SOT and gait metrics. All training and testing will be performed in a consistent and identical manner across all subjects in both groups.

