The **primary objective** of this sub-study is to investigate the cortical and non-cortical changes induced by CN-NINM training in patients with symptoms due to a mild to moderate TBI. In this sub-study, we will use functional magnetic resonance imaging (fMRI) tasks to identify the anatomical locations of the modulated neural activity induced by the tongue stimulation and how these changes can produce the behavioral and subjective improvements seen in patients with balance disorders after therapy with CN-NINM. A **secondary objective** is to evaluate the relationship between changes in brain and behavioral measures over time. We will evaluate the **hypothesis** that CN-NINM induces greater neuroplasticity in the Active than the Control group in areas involved in balance processing as well as by evaluation of major cranial nerves involving the tongue: trigeminal, CN-V, and facial, CN-VII and CN XII. An optic flow fMRI task will be used to evaluate areas involved in balance processing. A jaw-clenching fMRI task will be used to evaluate CN-V; A Tongue-thrust fMRI task will be used to evaluate CNV, VII, and CN-XII. This stimulation also has a cascading effect on neural activity in the brainstem (pons varolli and medulla), and cerebellum and higher order cortical structures such as the anterior cingulate. Neuroplasticity changes will be measured by task fMRI activation changes.

In addition to traditional task fMRI we will also use **advanced neuroimaging methods** to characterize functional and structural brain connectivity patterns in this population. **Resting state fcMRI** (rs-fcMRI) refers to the temporal coherence between different brain regions indicated by spontaneous blood-oxygen-level dependent fluctuations in the absence of any active task performance, i.e., when the brain is “at rest” [1-3]. Strong coherence has been identified between clinically relevant networks such as the somatomotor, visual, language, memory, and other functional networks and several studies have demonstrated test-retest reliability of rs-fcMRI measures. In a group of TBI patients in the sub-acute to chronic stage, Bonelle and colleagues recently showed that abnormality in default mode network (DMN) function is a sensitive marker of impairment of sustained attention [4].

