To identify abnormal structural connectivity patterns in the concussed brain we will collect Diffusion Tensor Imaging (**DTI**) data. DTI evaluates integrity of the white matter (WM) by exploiting the fact that water diffuses faster along the main axis (λ_1) of fibers compared with diffusion perpendicular to fibers (λ_2 and λ_3) [5-8]. Neuroplasticity changes over time from pre- to post-stimulation will be measured by functional connectivity as measured by rs-fcMRI and diffusivity and tractography measures as measured by DTI.

Methods

Sub-study Inclusion and Exclusion Criteria.

In addition to the inclusion and exclusion criteria in the main study, we will also exclude any subjects with contraindications to MR (e.g., claustrophobia, metal implants, etc.).

Subjects must also complete the MRI Screening Form (UWH# SR301436-DT [Rev. 02/17/14]) to determine final MRI Sub-study eligibility. The MRI Screening Form will be reviewed with subjects prior to each scanning session for any changes that could affect eligibility.

Total Subjects.

The sub-study will enroll 26 subjects (13 subjects in the Active PoNS™ group; 13 subjects in the Control group).

Consent Process.

After completion of the TBI Study consent, the Study Coordinator will also provide informed consent for the MRI Sub-study and explain that participation in the sub-study is optional. All candidates will be informed that declining participation in the MRI Sub-study will not affect their participation in the TBI Study. The PIs for both studies will be available to answer candidates' questions. All candidates are free to decline participation in either study without question if they so choose. Subjects will be given a copy of the signed consent form(s).

Compensation for Participation.

Subjects are eligible for the main TBI Study compensation; there is no additional compensation for completion of the MRI Sub-study.

[figure not shown]
Data Points

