Task fMRI: 1) In order to evaluate regions involved in balance processing, a checkerboard pattern will be used as the basis for a 2-dimensional visual stimuli in an optic flow task. A static checkerboard of alternating black and white squares will be used (CBstat) as the control stimulus. A rotating checkerboard (CBrot) will also be employed, in which the image appears to cyclically approach and recede relative to the observers' viewpoint, as well as rotate about the center of the viewfield [22]. During the scan, subjects will be shown the visual stimuli using a pseudo-randomized block-design paradigm. Each stimulus will be displayed for twelve seconds in blocks of three to six repetitions. Within a block, the stimulus presentations will be separated by six seconds of fixation to reduce the contamination of neural responses from one stimulus presentation into the next [23]. Each block will be separated by six seconds of fixation. The order of stimulus presentation will be the same for all subjects. Task scan will be approximately 7-8 minutes. **2)** In order to evaluate CNV, subjects will perform a jaw-clenching task, in which subjects will alternate between 20 seconds of jaw-clenching and 20 seconds of rest for a total of 6 cycles or 4 minutes. **3)** In order to evaluate CNV, VII, CNXII, subjects will perform a tongue thrust task in which they will alternate between thrusting their tongue to the roof of the mouth for 20 seconds and 20 seconds of rest for a total of 6 cycles or 4 minutes. We will also evaluate relationship of these brain MRI measures with balance and gait measures for the two treatment groups at each of the four time-points.

Each fMRI sub-study scan will take approximately 60 minutes to complete. All MRI scans will be performed at the Wisconsin Institutes for Medical Research (WIMR), [name].

Statistical Analysis

Task MRI Outcomes: Percent signal change will be computed for specific ROIs based on our previous work [11]. A repeated measures ANOVA will be used with Time (pre-intervention, stage 1, 2 3) as factor to examine change in percent signal over time in the patient group. To assess specific changes due to our intervention, we will perform paired t-tests (pre-intervention & stage 1; pre-intervention & stage 2 etc.). 2-sample t-tests will be used to compare differences between the Active PoNS group and control group.

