Resting fcMRI Outcomes: The output from the NBS toolbox is a network of brain regions that are significantly impaired between groups (identified using 2-sample t-test) and networks that are significantly influenced by the intervention over time ((identified using paired t-test) [18, 19]. For each significant network, the toolbox provides a list of all pairwise regions and their connection strengths and the t-statistic associated with each connection.

DTI outcomes: DTI analysis will yield whole brain fractional anisotropy (FA), and diffusivity measures (radial, axial, and mean diffusivity). A repeated measures ANOVA will be used with Time (pre-intervention, stage 1, 2 3) as factor to examine change in FA and diffusivity measures over time. 2-sample t-tests will be used to compare differences in these measures between the Active PoNS group and control group.

Brain Behavior correlations: A Pearson correlation or Spearman rank correlation test, as appropriate, will be used for correlation analyses between brain measures (task fMRI derived percent signal change, resting fcMRI derived connectivity measures, DTI FA and diffusivity measures) and behavioral outcome measures

Potential Risks and Benefits

Functional MRI: MRI, a Class II device, is recognized as a Non-Significant Risk (NSR) device by the FDA. All the systems, features, and accessories that will be used in the scanning of subjects under this protocol will be operating outside the limits identified by the FDA as “Criteria for Significant Risk Investigations.”

Risks

1. MRI: Aside from the standard risks associated with persons with certain metallic implants discussed above, no known risks of MRI exist. We know of no risks or adverse effects from the magnetic fields or radio waves used in the standard MRI pulse sequences. A small increase in risk may be associated with rapid gradient waveform switching times associated with fast MR imaging. In certain situations, the rapid switching of gradient waveforms has caused peripheral nerve stimulation in subjects. Significant nerve stimulation, however, has not occurred as long as the imaging system has been programmed to stay within certain limitations of gradient strength and switching time (dB/dt). The MR scanners currently being used at the UW stay within these guidelines, and any additional pulse sequences which we program in our

laboratory will be designed to stay within the current guidelines for dB/dt established by the FDA.

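### MRI sub-study: paired pre-post tests are used to credit change to the intervention although both arms train alike, and the planned between-arm tests name neither change from baseline nor a scan

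*Protocol*

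**What the plan says.** The addendum sets a between-arm hypothesis: "that CN-NINM induces greater neuroplasticity in the Active than the Control group in areas involved in balance processing". The main protocol's Study Design section says "All training and testing will be performed in a consistent and identical manner across all subjects in both groups".

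The addendum's Statistical Analysis section then plans as follows.

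- **Task fMRI.** A repeated-measures ANOVA takes Time "as factor to examine change in percent signal over time in the patient group". Next comes "To assess specific changes due to our intervention, we will perform paired t-tests", comparing the pre-intervention scan with each later stage. The following sentence adds "2-sample t-tests will be used to compare differences between the Active PoNS group and control group".
- **Resting connectivity.** Earlier in the addendum this is given a role in measuring change: "Neuroplasticity changes over time from pre- to post-stimulation will be measured by functional connectivity as measured by rs-fcMRI". The analysis text has two parts. The first is "The output from the NBS toolbox is a network of brain regions that are significantly impaired between groups (identified using 2-sample t-test"; the second is "networks that are significantly influenced by the intervention over time ((identified using paired t-test".
- **DTI.** An ANOVA on Time, then two-sample t-tests of the DTI measures between the two device groups.

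The sample size paragraph claims 85% power for an effect of 1.2 SD with 13 per group by two-sample t-test, and describes the comparator as healthy controls. The main protocol's Study Design section and the addendum's Total Subjects paragraph enrol only main-study TBI subjects, 13 on each device. The SAP does not cover the sub-study.

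**The concern.** The paired tests carry causal wording, but a within-subject comparison has no control. Subjects in both arms train intensively for 14 weeks and are scanned four times. Any change that training, practice, elapsed time or scanner drift produces in both arms would be picked up by the paired tests and, on the addendum's wording, reported as due to the intervention. The text does not say whether these tests are run by arm or pooled, and the problem is the same either way. An ANOVA with Time as its only stated factor has no Group-by-Time term, so it does not help.

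The tests that could answer the hypothesis are the two-sample ones, and they are under-specified. If the paired tests are read as the evidence of effect and the two-sample tests as a side comparison, the sub-study could report training or repeat-scan effects as device effects.

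**Working it through.** **1. The three outcomes side by side.**

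| Outcome | Within-subject analysis | Between-arm analysis | Stated as change from baseline? | Scan named? |
|---|---|---|---|---|
| Task fMRI | Time-only ANOVA; paired t-tests, credited to the intervention | Two-sample t-test | No | No |
| Resting connectivity (NBS) | Paired t-test, credited to the intervention | Two-sample t-test for impaired networks | No | No |
| DTI | Time-only ANOVA | Two-sample t-test | No | No |

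There are three post-baseline scans (end of Stages 1, 2 and 3). The task outcome, percent signal change, is computed per region and its change over time is then examined. The name alone therefore does not mean change from baseline. For resting connectivity, the word chosen for the between-group result (impaired) describes a state rather than a change, so the gap is widest there.

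**2. The plan's own power figure.** Inputs from the addendum: 13 per group, 1.2 SD, two-sided 0.05. Noncentral t with df = 24 and noncentrality 1.2 × √(13/2) = 3.06 gives 83.5%; the normal approximation gives 86.4%. The stated 85% lies between them and is not in question. Renaming the comparator leaves it unchanged.

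**3. Paired test with no device effect.** Assume both arms change by the same amount g, in SDs of change. The documents give no g, so 0.3, 0.5 and 0.8 are assumed. The paired t-test has df = n − 1 and noncentrality g√n (two-sided 0.05).

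| g | n = 13 (one arm): noncentrality, P(significant) | n = 26 (pooled): noncentrality, P(significant) |
|---|---|---|
| 0.3 | 1.08, 17% | 1.53, 31% |
| 0.5 | 1.80, 38% | 2.55, 69% |
| 0.8 | 2.88, 75% | 4.08, 97% |

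Simulation (200,000 trials) agrees: 17.1%, 38.1% and 75.4% at n = 13, and 31.5%, 68.9% and 97.4% at n = 26.

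**4. Two-sample t-test on change, same setting.** The noncentrality is (g − g) × √(13/2) = 0, so the rejection rate is the nominal 5% for every g. Simulation gives 5.0%, 5.0% and 4.9%.

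**5. Which SD the 1.2 refers to.** The addendum does not say. If it is the SD at a single scan, the SD of change is that SD × √(2(1 − r)), where r is the pre-post correlation. The documents give no r, so a range is assumed:

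- r = 0.3: 1.2/1.183 = 1.01 SD of change, power 70%
- r = 0.5: 1.2/1.000 = 1.20, power 84%
- r = 0.7: 1.2/0.775 = 1.55, power 97%

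Once the test is stated to be on change, the scale of the 1.2 needs stating too.

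**The case against.** - **Between-arm tests are planned.** A reader might infer from the paired-test wording that the sub-study has no Active-versus-Control comparison, or none for resting connectivity. The documents do not support that. All three outcomes have a two-sample test, and as only two groups are enrolled, the resting comparison most naturally means Active versus Control. Under randomisation, a two-sample test at a post-baseline scan is valid even on levels. This stands: the fault is attribution and under-specification, not absence.
- **Change may be intended for task fMRI.** The addendum's objectives tie neuroplasticity to changes in task activation, next to the Active-over-Control hypothesis. That partly supports a change reading, but the analysis section does not say so and still names no scan.
- **Intervention may mean the whole package.** The main protocol describes the CN-NINM intervention as including exercise, balance, gait and breathing training. On that reading a paired test does not by itself credit the stimulation. Time and repeat-scan effects remain uncontrolled, however, and the hypothesis concerns the difference between devices.
- **The sub-study is optional and mechanistic, in a trial that calls itself a pilot.** True, and it limits the stakes. But the addendum states a hypothesis, a primary outcome and a power calculation, so its wording should fit the design.

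**Conclusion.** The point holds as a should-fix matter of wording and specification. The paired tests and Time-only ANOVAs cannot support a statement that a change is due to stimulation, and the two-sample tests that can do so do not say what they compare or when.

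The size rests on an assumed shared change of 0.3 to 0.8 SD with no device effect. A single paired test is then significant in 17% to 75% of trials within one arm, or 31% to 97% pooled, against about 5% for a two-sample test of change. These rates are for one region in task fMRI. They should not be carried over to the resting analysis, where NBS controls family-wise error across the connectivity matrix. That control deals with multiplicity, not with change shared by both arms, so the attribution problem remains there without a figure attached.

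A reader might also infer that the reference to healthy controls, or the small gap between 83.5% and 85%, makes the power claim wrong. Neither does. The first is a wording conflict with the enrolment text and the second is within rounding. Nothing here touches the main trial's SOT analysis.

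**What to change.** 1. **Statistical Analysis (task fMRI, resting connectivity, DTI).** State that the test of device effect is the planned two-sample comparison, Active versus Control, of each subject's change from baseline. For resting connectivity this is the two-sample NBS test on change in connectivity; for task fMRI and DTI, ANCOVA on baseline is an alternative. Name one primary post-baseline scan for all three outcomes before unblinding, and label the other scans exploratory.
2. **Same section, wording.** Where the text has "To assess specific changes due to our intervention, we will perform paired t-tests", replace the opening purpose clause with: to describe change over time. Where it has "networks that are significantly influenced by the intervention over time ((identified using paired t-test", describe the networks simply as those that change over time. Label the paired tests and the Time-only ANOVAs descriptive.
3. **Sample size consideration.** Call the comparator the Control-device group, and say whether the 1.2 SD is the SD of change.

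The cost is addendum wording and slightly more analysis, mainly an NBS run on change scores from scans already planned. The sponsor gives up confirmatory use of the other scans. No extra subjects or scans are needed.

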1.0 BACKGROUND

This is a randomized clinical trial (RCT) in cranial nerve non-invasive neuromodulation (CN-NINM) using PoNS™ for treatment of symptoms due to mild to moderate traumatic brain injury (mTBI), post-concussive sequelae, (PCS) and post-traumatic stress (PTS). The study will involve training of both balance and gait, with assessments using standardized and relevant metrics to monitor changes in these indications, as well as cognitive function, sleep, headache, anxiety, mood, and eye-movement control.

1.1 Study Objective

The primary objective of this study is to demonstrate that CN-NINM training using the PoNS™ device with normal stimulation is more efficacious than training using a very low but perceivable stimulation device (Control) in subjects with symptoms due to the mild to moderate traumatic brain injury (TBI).

In this experimental investigation, data will be generated to describe the mean changes in balance and gait behavior from baseline for two treatment groups. The results will help to design and power the subsequent, incremental studies investigating the clinical efficacy of this intervention. Standardized clinical assessment mechanisms will measure changes in balance, gait, cognition, emotional function, headache, eye movement, and sleep in individuals with post-concussive and post-traumatic stress complaints in a 14-week rehabilitation program and after a 12-week withdrawal period.

1.2 Study Design

This is a randomized double blind study that will enroll up to 44 subjects (males and females) with identified balance deficits that will be equally distributed (1:1) into 2 subgroups: an “Active” CN-NINM device (PoNS™) group, and a “Control” (very low stimulation) device group.

The study will be run for a total of 26 weeks, consisting of three stages:

- a) The first stage consists of twice-daily in-lab training (ITP) for 2-weeks (with at-home training during the intervening weekend). The intensive CN-NINM training program will focus on balance and gait.
- b) The second stage will consist of subjects performing the same training for 12 weeks during Stage 2 – the Home Training Program (HTP). During this second stage, subjects will return to the lab 1 time per week for a training session.
- c) After completion of the second stage, subjects continue in the third stage, the withdrawal stage, where they no longer use the PoNS™ device for 12 weeks.

2.0 STUDY POPULATION

Subjects presenting with a chronic balance deficit due to mTBI. Subjects who also present with other symptoms, such as gait disturbance, mild to moderate recurrent headaches, sleep, memory, attention, or cognitive deficits, will be considered for participation. All candidates will have had a closed-head, non-penetrating, blunt, whiplash, or explosive blast-induced brain injury. Subjects will be required to provide their most recent neuroradiologic report and evidence of having completed a prescribed therapeutic regiment for their symptoms.

3.0 STATISTICAL CONSIDERATIONS

3.1 Sample Size Calculations

This study is an investigation to discover changes in the Composite SOT scores of subjects from baseline at the end of Week 2 and Week 14 visits in Active and Control groups.

The sample size for the study is based on the primary endpoint of change in mean SOT score from baseline at the end of Week 2 and Week 14 visits. The following assumptions are made:

- Control group response is half of that of the Active group
- Two-sided Test
- Equal variances in both groups
- Alpha Level= 0.05
- Power = 80%
- μ_{A1} = Mean change in SOT score from baseline to the end of Week 2 visit in Active group
- μ_{A2} = Mean change in SOT score from baseline to the end of Week 14 visit in Active group.
- μ_{C1} = Mean change in SOT score from baseline to the end of Week 2 visit in Control group
- μ_{C2} = Mean change in SOT score from baseline to the end of Week 14 visit in Control group.

To calculate the sample size, the following two hypotheses, Null (H_0) and Alternative (H_A) are formulated:

$$H_0: \mu_A = 2\mu_C \quad \text{VS.} \quad H_A: \mu_A \neq 2\mu_C$$

Since there is very limited experience on PoNS™ device and no data on control device, to calculate a sample size for this study, the mean change of 26.3 in composite SOT score at the end of Week 2 visit from baseline from the pilot study is used. Also it is assumed that the Control group response will be half of that of the Active group and equal variability in both groups with common standard deviation of 13.2, a 50% coefficient of variation in the Active group.

Based on the above assumptions, a sample size of 17 subjects in each group will have 80% power to detect a difference between the Treatment PoNS™ group mean μ_A , of 26.3 and the Control group mean μ_C , of 13.2 assuming that the common standard deviation is 13.2 using a two group t-test with a 0.05 two-sided significance level.

Previous experience in two controlled pilot studies, a drop-out rate of not more than 25% is estimated. Therefore, using conservative approach, the sample size for this study is increased from 34 to 44 subjects with 22 subjects in each arm.

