- University of Wisconsin – Madison Health Sciences Human Subjects IRB.
- University of Wisconsin – Institute for Clinical and Translational Research – Data Monitoring Committee.

Coded data (results only) will be shared with the MRMC via secure email for purposes of informing future studies.

Statistical Considerations

Sample Size Estimation

This study will be an experimental investigation and will employ descriptive statistics to discover the mean changes from baseline for Control and Active, and then calculate true effect sizes and corresponding variances both within and between the two treatment groups. It is a first step in an iterative, incremental process to generate enough data to make reasonable power calculations in subsequent controlled studies. We believe this approach is justified because we have a very small data set from which to draw estimates of effect size, and none regarding a control group response. Our estimates are based on large changes in SOT scores in the previous pilot study involving 4 civilian subjects with mild to moderate concussive TBI using an Active device.

For this study we have assumed that the Control group response will be half that of the active group. Using a two-sample *t*-test to estimate the sample sizes of the experimental group and the control group, and assuming equal variances in the two treatment groups with $\sigma = 0.5$; a 2-tailed significance level, $\alpha = 0.05$; the true difference of the means = 0.5, and setting the power at 0.80, we calculate that a cohort of 17 subjects in each arm is sufficient. Based on our previous experience in two controlled pilot studies, we estimate a drop-out rate of not more than 25%. In using this conservative estimate, we believe the study is sufficiently powered at 22 subjects per treatment group (44 subjects total) to generate the data necessary to calculate effect sizes and cohorts in the future.

Primary Endpoints and Observational Measures

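### Allowing for 25% dropout takes 17 per arm to 23, not 22; at that ceiling the planned 44 subjects give about 79% power instead of 80%

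*SAP*

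**What the plan says.** SAP section 3.1 sizes the trial with a two-group t-test. The settings are "Alpha Level= 0.05", "Two-sided Test" and 80% power. For the Active arm, "the mean change of 26.3 in composite SOT score at the end of Week 2 visit from baseline from the pilot study is used". For the Control arm, "it is assumed that the Control group response will be half of that of the Active group", which the SAP rounds to 13.2. The "common standard deviation is 13.2 using a two group t-test with a 0.05 two-sided significance level". The result is 17 per group.

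The SAP then takes dropout to be at most 25% and, describing the step as conservative, concludes that "the sample size for this study is increased from 34 to 44 subjects with 22 subjects in each arm".

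The Protocol (Statistical Considerations, Sample Size Estimation) reaches the same 17 and 22 on a rescaled effect: SD 0.5 and "the true difference of the means = 0.5, and setting the power at 0.80". On losses it says "we estimate a drop-out rate of not more than 25" per cent. There the word conservative describes this dropout estimate.

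The Protocol's Missing Data section rules out replacing dropouts, giving the enlarged sample as the reason. It also rules out imputation and specifies a complete-case analysis with a sensitivity analysis. Neither document states the formula that takes 17 to 22.

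**The concern.** A dropout allowance should leave the required number of evaluable subjects when dropout reaches the rate allowed for. That means dividing by the proportion retained. Here the division gives 23 per arm, and the plan has 22.

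The enlargement is the only protection the plan has: it is the stated reason for not replacing dropouts, and complete-case analysis means that each missing outcome comes off the analysed number. There is also almost no slack at 17 per arm, where power is only just above 80%. What is at stake is whether the sample-size statement is correct at its own limit. The study is also meant to inform the sizing of later trials, where the same inflation step could be carried forward.

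**Working it through.** **Inputs.** From SAP 3.1: difference 26.3 - 13.2 = 13.1, SD 13.2 (standardised effect 13.1/13.2 = 0.992), two-sided alpha 0.05, 17 evaluable and 22 enrolled per arm, dropout ceiling 25%. From the Protocol: difference 0.5 and SD 0.5 (standardised effect 1.0). The effect size and SD are taken as given.

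**Power formula.** For n per arm, the noncentral t distribution with 2n - 2 degrees of freedom and noncentrality difference / (SD × √(2/n)).

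**Step 1: reproduce the plan's 17.** At n = 17 the noncentrality is 13.1/(13.2 × √(2/17)) = 2.89 on 32 degrees of freedom, giving 80.1% power (80.7% with the Protocol's inputs). At n = 16 the SAP inputs give 77.5%. So 17 is the smallest number that reaches 80%, and the plan's figure is right.

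**Step 2: inflate for dropout.**
- Required per arm: 17/(1 - 0.25) = 17/0.75 = 22.67, rounded up to 23 (46 in total).
- 17 × 1.25 = 21.25, which rounds up to the plan's 22.
- 16/0.75 = 21.33 also rounds up to 22; 16 per arm is what a normal approximation gives.

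The plan's 22 is therefore consistent with multiplying by 1.25, but that is not the only route to it.

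**Step 3: what 22 per arm retains.**
- At 25% loss: 22 × 0.75 = 16.5 per arm, or 33 in total against the 34 required.
- Largest loss that leaves 17: (22 - 17)/22 = 5/22 = 22.7%.

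**Step 4: power.**

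| Situation | SAP inputs | Protocol inputs |
|---|---|---|
| 22 per arm, no loss | 89.5% | 90.0% |
| 17 per arm left (22.7% loss) | 80.1% | 80.7% |
| 16.5 per arm left (25% loss) | 78.9% | 79.5% |
| 22 per arm, averaged over random 25% dropout | 78.2% | 78.8% |
| 23 per arm, averaged over random 25% dropout | 80.1% | 80.7% |

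The value at 16.5 per arm is an interpolation. A real 16/17 split gives 78.8% (SAP inputs). The averaged rows treat each subject as dropping out independently with probability 0.25.

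**The case against.** The strongest reply is that 25% is a ceiling and not an expected rate. At lower losses the plan meets its target: at 20% loss, 17.6 per arm remain and power is about 81.5%; at 15%, 18.7 remain and power is about 83.9%. The shortfall exists only between 22.7% and 25%. This stands and keeps the point small. But an allowance for losses of up to 25% ought to hold at 25%.

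The gap is also smaller than the uncertainty in the inputs. The SD is an assumed 50% coefficient of variation and the Control response is an assumed half. Raising the SD from 13.2 to 13.7 at 17 per arm lowers power to 77.1%, a larger fall than the one at issue. This too stands. It argues against enlarging the trial, not against correcting the sentence.

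The Protocol ties 80% power to 17 per arm. It says of 22 per arm only that the study is adequately powered to produce data for later sizing. The SAP links the two more closely, because its step to 44 follows directly from the dropout rate. Still, neither document states outright that 44 subjects give 80% power at 25% loss.

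Dropout from treatment need not mean a lost outcome. The Protocol promises efforts to obtain follow-up data after withdrawal. The sizing effect is the Week 2 change, and the documents do not say at which visit the 25% applies. Actual outcome loss at Week 2 could be lower. That may reduce the shortfall in practice but does not make 22 the right result of the stated calculation.

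A reader might infer that the sponsor used the wrong inflation formula. No formula is given, and 22 can be reached in more than one way, so this remains a likely explanation only. A reader might also infer that the Protocol's use of the word conservative is mistaken. There it describes the dropout rate, which is an upper bound, and it can stay.

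**Conclusion.** The arithmetic point holds: 17 per arm with a 25% allowance gives 23 per arm, and 22 falls one subject per arm short. At the ceiling, power is 78.9% to 79.5%, or 78.2% to 78.8% averaged over random dropout, against the planned 80%.

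This is a minor misstatement. It does not support reading the trial as underpowered, or as failing at the dropout the sponsor expects: with no more than five outcomes lost per arm, the target is met on the plan's own assumptions. Nor does it show that recruitment must rise to 46.

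The conclusion assumes the documents' effect size and SD, equal losses in the two arms (or independent random loss for the averaged figures), dropout that means a missing primary outcome, and complete-case analysis without replacement.

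**What to change.** Keep 44 subjects. In SAP 3.1 and in the Protocol's Sample Size Estimation section, replace the sentence that links the dropout rate to 22 per arm with wording such as: *22 subjects per arm provide at least 80% power for loss of outcome data of up to about 22.7% per arm; at the 25% upper bound, power is about 79%.* In the SAP only, delete the phrase presenting the enlargement as conservative.

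The cost is one sentence in each document and a slightly less favourable power figure. Enrolment, randomisation list, procedures and analysis do not change.
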